6.8.2 Generalized Anxiety Disorder-7¹²

The GAD7 is a self-rated questionnaire assessing current anxiety levels. See APPENDIX 8 for an example of the GAD7.

7 STUDY MEDICATIONS, TREATMENT AND DOSING REGIMEN

7.1 Investigational medicinal product

7.1.1 Drug product

MT-8554 capsules and matching placebo are white capsules with no identifying mark. MT-8554 capsules contain [] mg, or [] mg of MT-8554 drug substance per capsule.

Bulk capsules will be packed in double polyethylene bag in stainless steel drum. Individual subject doses will be packed in blister wallets, labeled, and QP certified by []

MT-8554 and matching placebo capsules are manufactured, tested, and released according to Good Manufacturing Practice. All labeling will comply with applicable regulatory requirements. The Sponsor will provide the necessary documentation, such as a Certificate of Analysis or Quality Control release document.

7.1.2 Study drug supply

The Sponsor will provide MT-8554 to each site for each subject for the duration of their participation in the study. The Investigator, Study Nurse, or hospital pharmacy will dispense MT-8554 capsules at study visits according to protocol. A sufficient quantity of the appropriate strength MT-8554 capsules ([] mg, [] mg, and placebo) will be dispensed consistent with each subject's daily dosage requirement. Subjects should be instructed to bring their study medications with them to each visit and the Investigator or Study Nurse will perform a capsule count to ensure the subject has a sufficient supply of medication to last until the next scheduled visit. Subjects must return all study drugs remaining in their possession to study staff at the Week 12 visit.

7.1.3 Formulation, packaging, site storage, and labeling (MT-8554)

Capsules will be provided in []. Study drug will be provided to the study sites [] and should be stored according to the investigational medicinal product (IMP) clinical label.

MT-8554 capsules must be dispensed []. Subjects will be instructed to store the medication per the IMP clinical label.

Documentation for MT-8554 capsules will include, but may not be limited to, the following information:

- Receipt date
- Description of drug package, and drug product
- Lot/Batch/Code/other
- Expiration and Manufacturing dates
- Dispensing information
- IND number
- Certificate of Compliance

7.1.4 Shipping, receipt, handling and storage

On receiving a shipment of finished study medication at the Investigator site, the Investigator or designee will conduct an inventory check and complete a supplies receipt document, the original of which will be retained at the Investigator site; a copy must be returned to the Sponsor or designee. The Investigator or designee will maintain a record of all study medication received and returned.

Study medication at the Investigator site will be stored according to the conditions stated on the IMP clinical label in a locked, restricted-access area. A temperature log recording the daily continuous temperature of the storage area will be maintained (including weekends). Any study medication storage temperature deviations will be reported to the Sponsor.

7.1.5 Dispensing

At each visit, the Investigator or designee will provide the subject with the allocated dose. A record of the study medication dispensed to each subject will be maintained by the Investigator or designee in a Drug Accountability Log. Any opened wallets will not be re-dispensed.

7.1.6 Study drug accountability

The Investigator or designee must maintain an accurate record of the shipment and dispensing of study drug in a Drug Accountability Log. Drug accountability will be noted by the field monitor during site visits and at the completion of the study. Subjects will be asked to return all unused study drug and packaging on a regular basis, at the end of the study or at the time of study treatment discontinuation.

7.1.7 Disposal and destruction

At study close-out, and as appropriate during the course of the study, the Investigator will return all used and unused study drug, packaging, drug labels, and a copy of the completed Drug Accountability Log to the Sponsor's designated monitor or to the address provided in the Investigator Binder at each site.

The study drug supply may only be destroyed at the designated Sponsor facility or third party, as appropriate.

7.2 Dosing

Subjects are to self-administer study medication once daily before bedtime.

MT-8554 and placebo capsules should be swallowed whole with approximately 8 oz of water (subjects may drink an additional 8 oz of water if they have difficulty swallowing the capsules). The capsules must not be chewed, crushed or divided.

7.3 Compliance

The prescribed dosage, timing and mode of administration of study medication may not be changed. Subjects will be asked questions regarding the compliance, any departures from the intended regimen must be recorded in the eCRF.

Study medication accountability and subject compliance will be documented throughout the Placebo Run-in and Double-blind Treatment periods using study medication dispensing and return record forms. For Subjects who do not return their medication cards, the site will question them to determine compliance.

Subjects will be asked to return all unused medication including empty and partially used wallets. Study medication dispensed at the previous visit will be retrieved by the Investigator.

Non-compliance is defined as taking [REDACTED] of study medication during any evaluation period (visit to visit).

7.4 Subject identification

Each subject will be assigned a unique Subject Number at the Screening visit. At the point of randomization, each subject will receive a unique Randomization Number. Both the Subject Number and the Randomization Number will be documented in the subject's source documents. The Subject Number will be used to identify subjects in the study.

Re-screened subjects will be assigned a new Subject Number.

A list identifying the subjects by their Subject and Randomization Numbers will be kept at the Investigator site.

7.5 Procedures for assigning subjects to treatment groups

Randomization will take place after confirmation of inclusion/exclusion criteria prior to dispensing the first study medication on Day 1. Subjects will be randomly allocated on a 1:1:1:1 basis to 1 of 4 treatments (Section 3.1). Subjects will be randomized with IVRS/IWRS system.

7.6 Maintenance of the study blind and unblinding

In the single-blind Placebo Run-in period, Investigator site personnel will know that the study medication is placebo; however, subjects will not.

During the Double-blind Treatment period, neither the subject nor Investigator site personnel will know which treatment is being taken. Each subject's treatment will be given a unique code number, traceable to the identity, dose and batch number of the study medication. The IVRS/IWRS system will be used to hold treatment codes for each subject. The codes will only be accessible to authorized IVRS/IWRS users.

The IVRS/IWRS should not be accessed to break the treatment code for reasons other than safety or in an emergency. Should the Investigator wish to break the code for such reasons, he/she should consult the Sponsor (or designee) in advance. If this is not possible, the Investigator may access the IVRS/IWRS to obtain the treatment code and provide the system with the reason for breaking the blind. The Sponsor should be notified as soon as possible thereafter. If the blind is broken for any individual subject, the subject must be withdrawn from the study, and any procedures accompanying withdrawal should be performed (Section 4.5).

Because PK analysis will only be performed on samples from subjects receiving active drug, unblinded randomization codes will be given to PK lab.

Mitsubishi Tanabe Pharma Development America, Inc.
MT-8554-A01
MT-8554 for Reduction of Vasomotor Symptoms in Postmenopausal Women

An electronic list of randomization codes will be retrieved from IVRS/IWRS and transferred to the Sponsor at the end of the study.

MT-8554 and placebo are identical in appearance and will be packaged identically and suitably labeled to maintain the blind.

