9.3 Data processing

The data collected on the eCRFs will be captured in a specially constructed and validated database. The data will be validated using both manual and electronic means. Clarification of data will be requested from the Investigator site as required. An audit trail of the original database entries, changes and deletions, session dates and times and the credentials of the database user who performed the operation will be maintained by the system. The completed database will be quality assured and locked to prevent further changes. A full database extract, including electronic VMS diary data, will be made available for statistical analysis according to the methods outlined in Section 10 and the SAP.

AEs and medical history entries will be coded using the Medical Dictionary for Regulatory Activities (MedDRA). Concomitant medications will be coded using the World health Organization (WHO) Drug Dictionary. Versions of the dictionaries used will be documented in the data management plan and SAP.

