10.3 Statistical analysis

10.3.1 General considerations

A SAP containing definitions of analysis populations and baseline points, detailed data handling, analysis methods, detailed methods and criteria for the interim analysis, and

outputs (tables, figures and listings) will be developed and approved prior to database lock. Additional analysis may be performed if deemed necessary. Any deviations from the planned analysis will be described and justified in a separate document and in the CSR.

The statistical analysis will be performed using SAS® Version 9.2 or higher. The ITT population will be used for all clinical efficacy analysis; the PP population will also be used for the primary and secondary endpoints for confirming robustness. The Safety population will be used for all safety summaries. PK assessments will be performed using the PK population. All formal statistical tests will be done at the 5% two-sided significance level. Point estimates will have 2-sided 95% confidence intervals (CIs) where applicable.

Where appropriate, variables will be summarized descriptively (frequency and percent will be summarized for categorical variables; mean, standard deviation [SD], median, minimum, and maximum will be presented for continuous variables) by study visit and by treatment group.

All individual subject data will be listed, where applicable.

Baseline for VMS frequency is the sum of the number of moderate and severe VMS recorded in the daily VMS diary between Day -7 and Day -1, divided by the number of days with data. Baseline for VMS severity is the defined value (see below) between Day -7 and Day -1.

[figure not shown]
A daily severity score of zero (0) will be assigned if it will be reported that no VMS occurred on that day.

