11.8 End of study and site closure

The end of the study is defined as the last visit for the last subject. Upon completion of the study, or if the study or an Investigator site is prematurely discontinued, the following activities, where applicable, must be conducted by the Study Monitor in conjunction with the Investigator:

- Return of all study data to the Sponsor
- Completion of data clarifications and/or resolutions
- Accounting, reconciliation, and final disposition of used and unused study medication
- Review of Investigator site study records for completeness

Any unresolved AEs of SAEs will be followed according to Section 8.10.

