### **3.3 Final Analysis**

The final analysis will be conducted with unblinded data after database lock.

All the planned efficacy and safety analyses in this SAP will be performed by [REDACTED]

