## 6. SAMPLE SIZE AND POWER CONSIDERATIONS

## 7. STATISTICAL METHODOLOGY

### 7.1 Blinded Data Review

Prior to database lock, a blinded data review meeting (BDRM) will be conducted. Protocol deviations, protocol defined analysis populations will be confirmed during the meeting. Additional data handling rules may be introduced as results of data review. Should additional

data handling rules be confirmed during the meeting, they will be incorporated into the analyses planned in this SAP.

PK data that are considered "invalid" will be flagged in the listing. The PK data handling will be assessed during BDRM prior to database lock and in the investigation of PK data handling assessment after unblinding. A separate PK data handling document will be produced to cover both pre- and post- unblinding decisions. If PK sample handling errors or other factors identified after data unblinding and these errors have led to unexpected erroneous data, then these erroneous data will be regarded as "invalid".

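### Protocol 7.6 releases the randomization list to the Sponsor at the last subject's last visit, before database lock and possibly before the blinded data review

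*Protocol*

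**What the plan says.** Protocol 7.6, on maintaining the blind, ends with the release rule: "An electronic list of randomization codes will be retrieved from IVRS/IWRS and transferred to the Sponsor at the end of the study". It attaches no condition about database lock. Among those who must not know the treatment during the double-blind period, it names the subject and the site personnel, but not the Sponsor.

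Protocol 11.8 supplies the definition: "The end of the study is defined as the last visit for the last subject". Among the activities to be carried out on completion it lists "Completion of data clarifications and/or resolutions". Protocol 9.3 puts lock at the end of data processing: "The completed database will be quality assured and locked to prevent further changes".

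Protocol 10.3.1 says that the SAP "will be developed and approved prior to database lock". SAP 7.1 schedules the blinded data review meeting before lock. That meeting confirms protocol deviations and analysis populations, and "Additional data handling rules may be introduced as results of data review"; rules confirmed there are built into the planned analyses. For PK data, the same section distinguishes handling assessed at this meeting from handling assessed once the study is unblinded. SAP 3.3 adds: "The final analysis will be conducted with unblinded data after database lock".

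**The concern.** The release of codes is tied to one milestone (last visit), while the blinded review, SAP approval and unblinded analysis are tied to another (lock). The first comes earlier. Followed literally, Protocol 7.6 puts the full code list in the Sponsor's hands during the period that SAP 7.1 treats as blinded.

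The recipient is also the party that takes or influences the open decisions. SAP 1 says that Sponsor-side data science prepares the SAP and the clinical study team reviews it. SAP 9 has the Sponsor's statistics team take part in checking the outputs and has the Sponsor approve them. Neither document separates custody of the codes from these roles.

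What is at stake is the ability to show that pre-lock judgements were made without knowledge of treatment. Once the list has been released, that cannot be restored.

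**Working it through.** No arithmetic bears on the main question, and the plan states no figure to reproduce. The check is the order of events.

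1. **Last subject's last visit.** This is the end of study by Protocol 11.8, and therefore the code transfer by Protocol 7.6.
2. **Data clarifications.** Protocol 11.8 lists these as work upon completion, so at or after step 1.
3. **Blinded data review.** SAP 7.1 requires it only before lock. It may fall before or after step 1, but it confirms deviations and populations, so a date after the last visit is the natural reading.
4. **SAP approval.** Protocol 10.3.1 requires it only before lock, so the deadline also allows a date after step 1.
5. **Database lock.** Protocol 9.3 applies it to the completed, quality-assured database, so it follows step 2.
6. **Unblinded final analysis.** SAP 3.3 places it after step 5.

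Step 1 precedes step 5 on the protocol's own definitions, and nothing stops it preceding steps 3 and 4. SAP 7.1 implies that unblinding comes after step 3. That is the conflict.

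Next, what is still open between steps 1 and 5:

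- **ITT membership: essentially closed.** SAP 4.3 requires at least one post-baseline value of the primary endpoint.
- **Diary derivations: mostly closed.** SAP 5.4.1 and 5.4.2 fix the windows, the severity formulas and a rule for weeks with fewer than four diary days. That rule is worded permissively, which leaves a little room.
- **Per-protocol membership: open.** It depends on major deviations, for which the visible text gives no criteria, and the review meeting confirms them.
- **Added data handling rules: open**, by SAP 7.1.
- **Query resolution: open**, by Protocol 11.8.

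Last, how much data collection remains at step 1. Week 12 is nominally Day 85 and the follow-up call Day 115, a gap of 115 − 85 = 30 days. The call covers adverse events and medication, not efficacy. If the last subject takes the call, efficacy recording has ended about 30 days before the codes move, and some cleaning may be done. If the last subject instead enters the extension study, she has no follow-up call. Her last visit is then Week 12 and that margin disappears.

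**The case against.** The strongest reply is that the intent to stay blind is plain. SAP 7.1 calls the review blinded and separates its decisions from those made after unblinding. SAP 3.3 puts unblinded analysis after lock. Interim unblinded results go through the DMC's independent statistician (Protocol 10.3.3 and 11.3), and Protocol 7.6 limits code access within the IVRS/IWRS to authorized users. Protocol 7.6 does not cross-refer to 11.8 and may use the phrase loosely. It also does not say that the study team opens the list on receipt.

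The point about intent stands, and it rules out some stronger readings. A reader might infer that the Sponsor was unblinded at the review, or that the review is blinded in name only. That would need both early transfer and team access, and the documents show neither. A reader might also infer that every pre-lock decision is exposed, or that the self-reported diaries make the exposure severe. But diary entries are held as electronic source by a service provider (Protocol 9.1), recording is over by the last visit, and SAP 5 treats the per-protocol analysis as a sensitivity analysis. Nor can it be said that the SAP was approved after the codes moved: no approval date is visible, and Protocol 10.3.1 gives only a deadline.

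The reply does not remove the gap. The protocol defines the phrase it uses, and whoever sets up the code release could reasonably follow that definition. The access limit governs the system, and the transfer takes the list out of it. SAP 3.3 says when the analysis is run, not who may hold the codes beforehand.

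**Conclusion.** The point holds as a conflict between the protocol's release rule and the sequence the SAP relies on. Protocol 7.6, read with 11.8, permits the Sponsor to receive the codes before lock, and possibly before the blinded review, while queries, major-deviation and per-protocol decisions, and any added handling rules are open. There is no evidence that this happened or was planned.

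Severity is moderate. The code list covers all of the approximately 364 randomized subjects, but that is a headcount and not a measure of bias. The documents do not give the interval from last visit to lock, and the effect on any estimate cannot be quantified. No endpoint, model, significance level or sample size changes.

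The conclusion assumes that Protocol 7.6 uses the end of study as 11.8 defines it, and that no unseen document, such as a charter or an IVRS/IWRS specification, already holds the list back until lock.

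**What to change.** In Protocol 7.6, replace the end-of-study trigger with a conditional one: the list is transferred to the Sponsor *only after the SAP is approved, the blinded data review decisions are documented, and the database is locked*. State that Sponsor study staff remain blinded until then. Keep the exceptions the plan already provides for: unblinding for safety or in an emergency, the DMC's independent statistician, and the PK laboratory. Set the IVRS/IWRS release to the same conditions.

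The cost is one or two sentences and one system setting. No visit, subject burden or analysis is added.

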8 ADVERSE EVENT MANAGEMENT

All AEs and SAEs will be recorded in the source documents. All AEs and SAEs that occur from the time written informed consent is obtained until the end of the Safety Follow-up period (30 days after the last treatment visit) will be recorded in the eCRF. Even if the AE is assessed by the Investigator as not related to study medication, its occurrence must be recorded in the source documents and eCRF. AEs will be classified as 'baseline' if they occur before the administration of study medication.

AEs will be classified as 'treatment-emergent' if they arise following the first administration of study medication in the Double-blind Treatment period (after randomization) or if a pre-dose AE increases in severity following the first administration of study medication in the Double-blind Treatment period (after randomization).

At each study visit, after the subject has had an opportunity to spontaneously mention any problems, the Investigator should inquire about the occurrence of AEs. The questioning should be open-ended and non-leading.

8.1 Definition of an adverse event

An AE is any untoward medical occurrence in a subject or clinical investigation subject administered a pharmaceutical product that does not necessarily have a causal relationship with this treatment. An AE can therefore be any unfavorable and unintended sign (including an abnormal laboratory finding, for example), symptom, or disease temporally associated with the use of study medication, whether or not considered related to the study medication.

8.2 Definition of a serious adverse event

An SAE is defined as any untoward medical occurrence that at any dose:

- Results in death.
- Is life-threatening.
- Requires hospitalization or prolongation of existing hospitalization.
- Results in persistent or significant disability or incapacity.
- Is a congenital anomaly or birth defect.
- Is a medically important condition.

Medical and scientific judgment should be exercised in deciding whether an AE is serious and whether expedited reporting is appropriate in other situations, such as important medical events that may not be immediately life threatening or result in death or hospitalization but may jeopardize the subject or may require medical or surgical intervention to prevent 1 of the other outcomes listed in the above definition. These should also be considered serious. Examples of such events are invasive or malignant cancers, intensive treatment in an emergency room or at home for allergic bronchospasm, blood dyscrasias or convulsions that do not result in hospitalization, or development of drug dependency or drug abuse. These should also usually be considered serious.

The term 'life threatening' refers to an event/reaction in which the subject was at risk of death at the time of the event/reaction; it does not refer to an event/reaction which hypothetically might have caused death if it were more severe.

Admission to a hospital as a new inpatient is deemed as meeting this criterion, even when the length of hospital stay was less than 24 hours. Transfer to other departments of the same hospital due to a newly emerged event during the hospitalization (e.g., transfer from the psychiatry ward to the internal medicine ward, from the internal medicine ward to the coronary intensive care unit, or from the neurology ward to the tuberculosis ward) is also counted as hospitalization.

SAEs will be recorded and reported as described in Section 8.7.

